Fibromyalgia (FM) is a chronic pain syndrome with characteristic symptoms of fatigue, sleep disturbance, mood problems and cognitive complaints. Recent research suggests that the central nervous system (CNS) plays a major role in these symptoms in part through central sensitization [1,2]. Current medications for the treatment of FM have limited efficacy and are associated with side effects for most patients. Furthermore, polypharmacy is common in patients with FM, which potentially increases the side effect burden of treatment. e-TNS (external trigeminal nerve stimulation) with the CEFALY® device produces a sedative effect [3] and has proven its efficacy as a prophylactic treatment for episodic migraine [4,5]. The device is FDA-approved for the prevention of frequent episodic migraine and is very safe, with less than 5% of reported adverse events that are all minor and fully reversible. Besides its indication for migraine, e-TNS CEFALY® device shows several actions on the CNS that could support its use in FM: it produces a sedative effect during the session, pilot trials reported improvement in depression [6], and migraine patients frequently report improved sleep and less fatigue. Therefore e-TNS with CEFALY® might help to improve symptoms of FM and make available a new valuable therapeutic treatment for FM.

Prior to conducting a randomized sham controlled clinical trial to investigate the efficacy and safety of e-TNS with the CEFALY® device in FM, a pilot open trial is needed to collect preliminary data on efficacy and safety and to establish the group sizes for the subsequent controlled trials.

2. Study objective

The main objective of this clinical pilot trial is to evaluate the use of the CEFALY® neurostimulator as a therapeutic treatment for FM.

3. Study outcomes

Primary outcomes:

- Mean pain intensity between baseline and 12 weeks endpoint
- Fibromyalgia Impact Questionnaire-revised (FIQR) total score between baseline and 12 weeks endpoint

Secondary outcomes:

- Mean pain intensity between baseline and 4 weeks visit
- FIQR total score between baseline and 4 weeks visit
- Patient Global Impression of Change (PGIC) at 4 weeks visit and at 12 weeks endpoint
- EQ-5D-3L between baseline and 4 weeks visit; and between baseline and 12 weeks endpoint
- Patient Reported Outcomes Measurement Information System (PROMIS) measures for depression, fatigue and sleep between baseline and 4 weeks visit; and between baseline and 12 weeks endpoint
- Multiple Ability Self-report Questionnaire (MASQ) between baseline and 4 weeks visit; and between baseline and 12 weeks endpoint

Exploratory outcomes:

- FM30 ($\geq 30\%$ responder rate) i.e. meeting the following criteria:
 - $\geq 30\%$ reduction in pain (FIQR)
 - $\geq 10\%$ improvement in physical function
 - $\geq 30\%$ improvement in 2 of the following symptoms: (with FIQR) fatigue, sleep, depression, anxiety, (with MASQ) cognition
- FM20 ($\geq 20\%$ responder rate)
 - $\geq 20\%$ reduction in pain (FIQR)
 - $\geq 10\%$ improvement in physical function
 - $\geq 20\%$ improvement in 2 of the following symptoms: (with FIQ) fatigue, sleep, depression, anxiety, (with MASQ) cognition

4. Study design

4.1. General description

This study is a clinical study with the following characteristics:

- Single center
- Prospective
- Open

4.2. Experimental protocol

Patient diagnosed with FM will be screened for study eligibility. Eligible patients will be scheduled for the baseline visit (enrollment visit) that will take place within a maximum of 4 weeks after the screening visit. At the baseline visit, the patients will be given a CEFALY® device together with the necessary accessories for a 12-week treatment period. Outcome measures will be administered at the baseline visit, after 4 weeks of treatment and at the end of the 12-week treatment period. The overall study flow is illustrated in Figure 1.

4.2.1. Screening visit

The patients will be evaluated for study eligibility at the screening visit (Visit 1). They will receive study information and consent documents, and they have to sign these documents before study procedures are initiated. Then the investigator will verify that the patient meets all inclusion criteria and none of the exclusion criteria. If this is the case, the patient will be tested for tolerance to the neurostimulation (nociceptive threshold test). If the patient passes this test, he/she will continue in the study.

4.2.2. Baseline visit (enrollment visit)

The baseline visit (Visit 2) is scheduled within 4 weeks following the screening visit. If the patient still meets the inclusion criteria regarding the pain intensity, he/she will complete the baseline questionnaires. The patient will receive a CEFALY® device together with the necessary accessories for a 12-week treatment period.

4.2.3. Treatment period – intermediate and final visits

During 12 weeks, patients will apply the CEFALY® twice a day, roughly at the same time of the day everyday (morning and evening) for a complete treatment session of 20 minutes. Compliance will be analyzed afterwards using a built-in recording system. An intermediate visit will be scheduled after 4 weeks of treatment (between minimum 4 weeks and maximum 6 weeks) (Visit 3). The patient will complete the visit questionnaires to assess efficacy of the treatment, and report possible side effects and adverse events regardless of possible relationship to the device. A final visit will occur after the 12 weeks of treatment (between minimum 12 weeks and maximum 14 weeks) (Visit 4) to collect the

CEFALY® device and complete visit questionnaires to assess efficacy as well as possible side effects and adverse events reported regardless of possible relationship to the CEFALY® device.

[figure not shown]

Figure 1 - Study flowchart

5. Subjects

The study will include 50 men or women.

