6.4. Use during the trial

The CEFALY® will be used twice a day by the patient. The patients should have at least two sessions of stimulation per day, roughly at the same time of the day everyday (morning and evening). A complete treatment session lasts 20 minutes. The patient should therefore use the device 40 minutes a day.

The device contains a system that records the usage statistics (compliance). For each patient it will be possible to know how much time the device has been activated and at what intensity on average the patient has been stimulated.

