6.6. Device provisioning

The promoter will deliver the devices directly to the investigators.

The patient will receive the device at the baseline visit and will return it at the end of the 12-week treatment period during the final visit.

7. Practical study modalities

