8.2.2. Statistical methods

- All relevant general, safety and efficacy data will be descriptively summarized at each time point.
- Continuous data will be summarized by the number of subjects (N), the arithmetic mean, the standard deviation, the coefficient of variation as a percentage (CV%), the median, the inter-quartile range, the minimum and the maximum value.
- Categorical data will be summarized by absolute (N) and relative (%) frequency tables.
- Where considered as relevant, the study data will also be graphically depicted.
- Results analysis will be carry out on a per protocol basis, i.e. on $\geq 50\%$ compliant patients; sub-analysis will be performed as well on an intention to treat basis, i.e. including all subjects who used the study device at least once. For each patient, the average outcome will be calculated before and after the treatment period on all data available, without any imputation of missing data.

9. Management of adverse events

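### The leading week-4 results appear to be restricted to patients selected by device use over the whole 12-week course, including use after the week-4 visit

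*Combined protocol and SAP*

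**What the plan says.** Section 3 lists week-4 secondary outcomes, beginning with "Mean pain intensity between baseline and 4 weeks visit" and continuing with FIQR, PGIC, EQ-5D-3L, PROMIS and MASQ. Both primary outcomes are at week 12.

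On the analysis set, Section 8.2.2 says: "Results analysis will be carry out on a per protocol basis". It defines that set as patients with at least 50% compliance and adds an intention-to-treat sub-analysis of everyone who used the device at least once. It gives no period or denominator for the 50%, and no separate rule for week 4.

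On measuring compliance, Section 4.2.3 says: "Compliance will be analyzed afterwards using a built-in recording system". Section 6.4 describes what the recorder provides: "For each patient it will be possible to know how much time the device has been activated", together with average intensity. It mentions no breakdown by period. Section 6.6 has the patient receive the device at baseline and says that he or she "will return it at the end of the 12-week treatment period during the final visit". No read-out at Visit 3 is planned.

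**The concern.** A per-protocol set is meant to show the outcome in patients who received enough treatment before that outcome was measured. If one figure covering all 12 weeks decides who is in the set, membership for the week-4 result depends partly on what patients did after their week-4 scores were recorded.

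That later use may itself depend on the week-4 response. In an open study, patients who felt no benefit or tolerated the device poorly may be the ones who stop after Visit 3. Leaving out their fully exposed week-4 scores would make the leading week-4 result look better than it was. In the other direction, patients who hardly used the device before Visit 3 but used it well later would stay in, and their scores would say little about four weeks of treatment.

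The pilot is meant to supply preliminary efficacy data and group sizes for later controlled trials, so a distorted early estimate could be carried forward.

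**Working it through.** **Inputs from the documents**
- Section 4.2.3: "During 12 weeks, patients will apply the CEFALY® twice a day".
- Section 6.4: "A complete treatment session lasts 20 minutes" and "The patient should therefore use the device 40 minutes a day". Check: 2 × 20 = 40 minutes, so the plan's daily figure reproduces.
- Section 8.2.2: cut-off of 50%.
- Section 4.2.3: Visit 3 falls between weeks 4 and 6, Visit 4 between weeks 12 and 14.

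**Prescribed use.** Sessions = weeks × 7 × 2.
- Whole course: 12 × 7 × 2 = 168 sessions, or 168 × 20 = 3,360 minutes.
- Cut-off: 0.50 × 168 = 84 sessions, which is 84 / 14 = 6 weeks of full use.
- To week 4: 4 × 7 × 2 = 56 sessions. Weeks 5 to 12: 168 − 56 = 112 sessions.

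**Pattern 1: full use, then stops after a week-4 Visit 3.**
- Stops at once: 56 / 168 = 33.3%, left out.
- Stops just short of the end of week 6: 83 / 168 = 49.4%, left out.
- To be kept, the patient needs 84 − 56 = 28 of the later 112 sessions (25%).

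**Pattern 2: no use before a week-4 Visit 3.**
- Kept with 84 of the later 112 sessions (84 / 112 = 75%), since 84 / 168 = 50%.
- With full later use: 112 / 168 = 66.7%, kept.

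**Effect of the Visit 3 date (12-week denominator)**

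| Visit 3 at | Full use to Visit 3, then none | None to Visit 3, then full use |
|---|---|---|
| week 4 | 56/168 = 33.3%, out | 112/168 = 66.7%, in |
| week 5 | 70/168 = 41.7%, out | 98/168 = 58.3%, in |
| week 6 | 84/168 = 50.0%, in | 84/168 = 50.0%, in |

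At week 6 the first pattern disappears, and the second survives only with perfect later use. If the denominator ran to a week-14 Visit 4 (14 × 7 × 2 = 196 sessions), a week-4 Visit 3 would give 56 / 196 = 28.6% and 140 / 196 = 71.4%, and a week-6 Visit 3 would give 84 / 196 = 42.9% and 112 / 196 = 57.1%.

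**Same patients, compliance counted to week 4.** Cut-off 0.50 × 56 = 28 sessions. Pattern 1 has 56 / 56 = 100% and is kept. Pattern 2 has 0 / 56 = 0% and is left out. Both classifications reverse.

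**Possible size of the upward bias from pattern 1.** Let a share p of the patients stop in this way, with a mean week-4 pain change d points worse than the others' mean m. The mean over all is (1 − p)m + p(m − d) = m − pd. The mean without the stoppers is m, so the overstatement is p × d. The documents give neither p nor d. Assumed range: 0.10 × 1 = 0.1 points to 0.20 × 2 = 0.4 points on the 0-10 scale. Pattern 2 works in the opposite direction, and nothing in the documents allows it to be sized.

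**The case against.** The strongest reply is that the whole-course rule is never written down. Section 8.2.2 gives no window, and analysing compliance afterwards fixes when the figure is worked out, not the period it covers. If the log is dated, a read-out at the end could still yield exposure to Visit 3. This stands to the extent that the whole-course reading is an inference. It remains the natural one, because the plan describes a single assessment after treatment and one usage total per patient.

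It can also be argued that the per-protocol rule is not aimed at week 4. Section 8.2.2 first promises descriptive summaries at every time point without limiting them to compliant patients, and the per-protocol item goes on to speak of outcomes before and after treatment. The text is ambiguous here, but it names no other leading set for the week-4 outcomes.

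A reader might infer that the early stoppers' week-4 scores are lost. They are not: the intention-to-treat sub-analysis retains them. They are missing from the leading result only. Making that set lead would remove the selection, but if a per-protocol result is reported at all, its exposure window should still match its outcome.

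A reader might also infer that every full user who stops before the end of week 6 is wrongly excluded. That goes too far. Someone who stops in week 2 does not have full exposure to week 4. The argument covers only those who stop at or after Visit 3.

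Two further points stand. The patient with no use before Visit 3 is an extreme case of unknown frequency. Section 6.4 also asks for at least two sessions a day without saying whether extra ones count, so extra use could lift an early stopper's share; reaching 84 sessions in 28 days would, however, take 84 / 28 = 3 a day throughout.

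**Conclusion.** The concern holds in a limited form. On the natural reading, the leading week-4 results are conditioned on device use after the measurement. With Visit 3 at week 4, a full user who stops before the end of week 6 (56 to 83 of 168 sessions) is left out despite complete exposure, and a patient with little or no early use can be kept. The mismatch shrinks as Visit 3 moves towards week 6.

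This rests on three assumptions: compliance is one whole-course figure, it is counted against two sessions a day, and the per-protocol set applies at week 4. If another rule was intended, the plan still needs to state it.

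The size is unknown. The range of 0.1 to 0.4 points is an illustration on assumed stopping rates and differences. The documents do not support a claim that week-4 improvement is certainly overstated, since the two patterns pull in opposite directions. Nor do they support extending the point to the primary outcomes: at week 12, a whole-course figure matches the outcome. This is a weakness in secondary, descriptive results of an open pilot, worth correcting because the correction is simple.

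**What to change.** - In Section 8.2.2, define compliance for each outcome from baseline to the date of that assessment: use to Visit 3 for week-4 outcomes, use to Visit 4 for week-12 outcomes. State the denominator and whether sessions beyond two a day count.
- In Section 4.2.3, provide for reading the recorder at Visit 3 as well as Visit 4, or for splitting the final log by date. First confirm that the device allows one of these; the documents do not say.
- If neither is possible, present the week-4 outcomes primarily in the intention-to-treat set already planned.

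The cost is a short addition to each of the two sections and, if the read-out route is taken, a reading at an existing visit. A Visit 3 reading would also preserve an exposure figure for a patient whose device is never returned. The downside is that the week-4 and week-12 per-protocol sets may differ in membership, so week 4 should also be shown in the week-12 set, to allow a comparison in the same patients.

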5.1. Inclusion criteria

The following inclusion criteria apply:

1. Aged from 18 to 65 years
2. Diagnosed with FM according to the 2010 ACR Preliminary Diagnostic Criteria for Fibromyalgia [7]
3. Having a minimum pain score of at least 4 on the 0-10 FIQR pain scale at screening and baseline.

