7.1. Measures

The outcome measures taken in the study are all based on self-assessment questionnaires. The following will be used:

- FIQR: evaluation of the impact and the severity of FM symptoms.
- EQ-5D-3L: evaluation of the general quality of life.
- PROMIS for depression, fatigue, and sleep.
- MASQ: assessment of the self-perception of cognitive difficulties.
- PGIC: assessment of the patient perception of change induced by the treatment.

In order to evaluate the modification of pain level from baseline to 4-week treatment and to 12-week treatment, the item of the FIQR related to pain will be used, i.e. numeric rating scale (NRS) scoring the pain between 0 and 10.

During the screening visit, the following tests will be performed to evaluate the exclusion criteria 4 and 7, respectively:

- Beck Depression Inventory-Fast Screen (BDI-FS);
- Columbia Suicide Severity Rating Scale (C-SSRS).

The following table depicts at which visit the various questionnaires are completed.

	Visit 1 Screening	Visit 2 Baseline	Visit 3 Intermediate assessment (4-week treatment)	Visit 4 Final assessment (12-week treatment)
FIQR	● (*)	●	●	●
EQ-5D-3L		●	●	●
PROMIS		●	●	●
MASQ		●	●	●
PGIC			●	●
BDI-FS	●			
C-SSRS	●			

(*) Only the item of the FIQR related to pain.

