8.1. Data management

The data will be included in the case report form (CRF) that will be provided to the promoter anonymously, using a numbering system.

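### Does regression to the mean, arising because the pain entry threshold and the primary pain baseline use the same score, call for a change to the analysis?

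*Combined protocol and SAP*

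**What the plan says.** Section 5.1 (criterion 3) requires patients "Having a minimum pain score of at least 4 on the 0-10 FIQR pain scale at screening and baseline". Section 4.2.2 applies the threshold a second time at Visit 2: "If the patient still meets the inclusion criteria regarding the pain intensity, he/she will complete the baseline questionnaires". Section 3 lists as a primary outcome "Mean pain intensity between baseline and 12 weeks endpoint", and section 7.1 states that for the change in pain "the item of the FIQR related to pain will be used". So one 0-10 item decides entry and also supplies the baseline.

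The item is also collected at Visit 1; the footnote to the visit table in section 7.1 reads "Only the item of the FIQR related to pain". Consent comes earlier, since patients are told that "they have to sign these documents before study procedures are initiated" (section 4.2.1).

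Section 4.1 describes a single-centre, prospective, open study, and no control arm appears anywhere. Section 8.2.2 plans descriptive summaries at each time point and a before/after average per patient, without imputation. The main analysis set is patients at least 50% compliant, with a secondary analysis of everyone who used the device at least once. No hypothesis test, confidence interval or adjustment is specified. The introduction gives the purpose as preliminary data on efficacy and safety and "to establish the group sizes for the subsequent controlled trials".

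**The concern.** When patients are chosen because a noisy score is high, and that score then serves as baseline, the group mean tends to fall at the next measurement even if nothing is done. A parallel sham group would show the same fall and cancel it. Here there is none, so the fall adds to the apparent benefit of the device.

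Two consequences would matter. A reader who puts an interval around the mean change could see improvement where there is none. And if the raw change were taken as the expected difference from sham, the later controlled trial would be too small. The screening pain score is already collected, so it looks as though a simple correction has been missed.

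**Working it through.** **The plan's own figure.** The only stated figure is 50 patients (section 8.2.1). It comes with no effect size, SD, alpha, power or dropout rate, so it cannot be reproduced.

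**Inputs.** From the documents: threshold of at least 4 at Visits 1 and 2, a 0-10 scale, n=50. Assumed, because the documents give none: unselected mean 5, 5.5, 6 or 6.5; SD 1.5, 2 or 2.5; Visit 1–Visit 2 correlation *a* with correlation *b* of each with Visit 4, (*a*, *b*) = (.5,.5), (.6,.6), (.7,.7), (.7,.5), (.85,.5); zero treatment effect. That makes 4 × 3 × 5 = 60 scenarios. Scores were simulated as trivariate normal, then rounded and clipped to 0-10.

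**Size by formula.** Let *d* be the enrolled patients' mean baseline minus the unselected mean. Both visits are gated alike, so ignoring rounding and clipping the expected fall is about *d* × [1 − 2*b*/(1+*a*)].
- Mean 5, SD 2, *a* = *b* = 0.5: the enrolled baseline mean is 5.93, so *d* = 0.93 and the fall is 0.93 × (1 − 1/1.5) = 0.31. Simulation: 0.32.
- Mean 5, SD 2, *a* = 0.85, *b* = 0.5: *d* is about 0.94, and 0.94 × (1 − 1/1.85) = 0.43. Simulation: 0.43.

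**All scenarios.** The spurious fall is 0.02 to 0.63, median 0.18, middle half 0.10 to 0.30, with 15 of 60 reaching 0.3. At SD 2 it is 0.07 to 0.43. With an unselected mean of 7, outside that grid, the median is 0.08 and the maximum 0.24.

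**Against sampling error.** The 95% half-width is 1.96 × SD of change / √50: 0.42, 0.55 and 0.69 for change SDs of 1.5, 2 and 2.5. The artefact stays below its own scenario's half-width in all 60. The margin is thin at the extreme corner (mean 5, SD 2.5, *a* = .85, *b* = .5): with a change SD of about 2.3 the half-width is 1.96 × 2.3/7.07 = 0.64, against 0.63.

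**What an interval would do, if one were added.** At mean 5, SD 2 (.85,.5) the standard error is about 1.91/√50 = 0.27. The bias is 0.43/0.27 = 1.6 standard errors, so the interval lies wholly on the improvement side with probability about P(Z > 1.96 − 1.6) = 0.36; simulation gives 35%. At mean 6 (.7,.5) it is 12%, and at mean 6.5 (.7,.7) 5%. The nominal figure is 2.5%.

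**Can the screening scores already held remove it?** No. At mean 5, SD 2, correlation 0.5, the fall to week 12 is 0.321 from baseline, 0.323 from screening and 0.322 from their average. The screening-to-baseline change in enrolled patients is about 0.00, so subtracting it removes nothing either. Both scores passed the same threshold.

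**What could remove it.** A likelihood-based model for Visits 1, 2 and 4 that includes patients who failed the threshold. With no other selection its large-sample residual is at most about 0.01. Its costs are:
- At mean 5, SD 2, correlation 0.5, 65.1% pass both visits, so 50/0.651 − 50 = 27 extra patients' scores are needed per 50 enrolled. The range is 5 to 27 at SD 2 and 9 to 35 at SD 2.5.
- The standard error rises by 6% to 28%.
- The estimate refers to the unselected mean. If the true effect were a 20% reduction, it would understate the enrolled patients' effect by 0.06 to 0.10.
- It corrects only for the threshold. Suppose, as an illustration, that 50% of patients whose pain worsens by 2 or more reach the compliant set, against 90% of the rest. With zero effect and SD 2, the adjusted change in that set is still about −0.14 to −0.23 across the three scenarios above.

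**The case for a change.** The best case for acting is that the adjustment works on its own terms and is cheap. In trials of 50 with a true effect of −1 (mean 5, SD 2, .85/.5), the unadjusted change averages −1.42 and the adjusted one −1.01. Root mean squared error was lower in 8 of 9 scenarios and nearly equal in the ninth (0.228 against 0.225). The pain item must be scored at each visit to apply the threshold, so keeping failing scores needs little effort, and unrecorded scores cannot be recovered later.

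The statistical part of this stands. Three things weaken it as a reason to amend the plan. First, the set of patients excluded only by the pain criterion cannot be identified: section 4.2.1 tests tolerance to stimulation (exclusion criterion 11) only after the other criteria are met, so Visit 1 pain failures are never tested. If only Visit 2 failures were kept, 0.15 to 0.28 would remain at mean 5, SD 2 when correlation decays over time. Second, the model removes one uncontrolled component and leaves placebo response, natural course and selection by compliance. Third, statisticians could reasonably disagree about extrapolating to untreated patients scoring below 4 in order to describe an open pilot. The CRF is an annex that is not available here and may already record failing scores.

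A written warning against using the change as the sham difference would do no harm, but the plan nowhere proposes that use.

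**Conclusion.** The mechanism is real and favours the device, but no change to the plan follows. Under the assumed inputs the artefact is most likely a few tenths of a point or less (median 0.18, range 0.02 to 0.63). It is smaller if unselected pain averages 7, and it does not exceed the sampling uncertainty at n=50 in any scenario examined. That comparison does not make it negligible: near the top of the range an added interval would mislead in about a third of trials. The plan, however, attaches no interval or test to the change. A descriptive before/after result from an open pilot cannot support a claim about the device with or without this correction, because placebo response and natural course remain in it.

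Requiring the threshold at both visits and reporting a plain descriptive change is a fair trade-off for a study meant to precede a sham-controlled trial. If that trial uses the same threshold, its sham arm will carry the same artefact and cancel it. Analysts can be expected to name regression to the mean, alongside placebo response, when interpreting the fall. All magnitudes rest on assumed means, SDs and correlations.
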